## **STATISTICAL CONSIDERATIONS**

The proposed study is a 4-arm parallel group, open-label randomized clinical trial. The treatment arms, hydroxychloroquine alone (HCQ), hydroxychloroquine + azithromycin (HCQ + AZM), chloroquine alone (CQ) and chloroquine + azithromycin (CQ + AZM) will be randomly assigned eligible participants. The primary hypotheses in this study are whether the addition of AZM to either HCQ or CQ improve patient recovery rates.

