#### *Primary endpoint analysis*

The primary endpoint of this study is the time to recovery following the definition outlined in the STUDY AIMS/ENDPOINTS section. Our primary analysis will be to use Kaplan-Meier (KM) survival analysis to test the statistical null hypothesis that there is no difference in recovery rates between the non-AZM treatment arms and the AZM treatment arms (HCQ vs HCQ + AZM, CQ vs CQ + AZM). If either of the AZM arms have significantly faster recovery rates (two-sided  $P$ -value  $< 0.05$ ) compared to the corresponding non-AZM arm group, then we will conclude that the AZM group is superior to the non-AZM group. We will also compare recovery rates between the HCQ vs CQ, and HCQ + AZM vs CQ + AZM treatment arms to assess whether HCQ and CQ treatments differentially influence recovery. We will then proceed to a multivariable Cox-regression model that adjusts symptom severity at baseline (sum of presence of fever  $\geq 38.0^{\circ}\text{C}$  and total number of 'Quite a Bit' or 'Very much' responses to the Flu-PRO questionnaire [maximum total = 20]). The final model will retain the treatment groups and those covariates that are significant ( $P < 0.05$ ) in the multivariable model and we will report the model-adjusted hazard ratios and 95% CI for the treatment groups as well as the covariates. Participants that are lost to follow-up or die will be censored at the date of last contact or date of death, respectively, and patients that do not recover during the study period will be censored at 42 days. The primary analysis will be intention-to-treat and a per-protocol analysis will also be performed as a secondary analysis of the primary endpoint. Statistical analyses will be conducted using PROC LIFETEST and PROC PHREG as appropriate (SAS Institute Inc, Cary, NC, USA).

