#### **Sample size and power analysis**

Version 2.0. March 30th 2020

Page 18 of 18

A recent COVID-19 study in the Jiangsu province of China indicated that fever in about half of COVID-19 infected people lasted less than 7 days. Because this research area is rapidly developing and there is limited knowledge about this disease, we use the simple median estimate of 7-days as a starting point for our recovery outcome. In addition to attenuation of fever, our primary outcome adds criteria that fever must be attenuated for at least 48 hours and there needs to be symptom improvement. Given our criteria we assume 11 days as a rough estimate for median recovery time in the non-AZM treatment groups to compare the AZM treatment groups against in our study. This study is powered to test the hypothesis that HCQ + AZM improves recovery rate compared to HCQ alone, and CQ + AZM improves recovery rate compared to CQ alone. Assuming a minimum improvement of 4 days in the median recovery time (median recovery time of 7-days) and a censoring rate due to death or loss to follow-up of 0.04 per day, we plan on enrolling a total of 500 participants (125 per arm) which would give us just over 80 percent power ( $1 - \beta = 82\%$ ,  $\alpha = 0.05$ ) to test our primary hypotheses.

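### Concluding AZM superiority if either of two unadjusted primary comparisons succeeds gives a 4.9% chance of a false claim when AZM has no effect, against 2.5% for one test

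*Combined protocol and SAP*

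**What the plan says.** The opening of Statistical Considerations names more than one primary hypothesis: "The primary hypotheses in this study are whether the addition of AZM to either HCQ or CQ improve patient recovery rates".

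Primary endpoint analysis then frames a single null hypothesis of equal recovery with and without AZM. It examines this in two pairs, HCQ vs HCQ + AZM and CQ vs CQ + AZM, each at a two-sided P-value below 0.05. The decision rule begins "If either of the AZM arms have significantly faster recovery rates" and continues, after the P-value threshold, "compared to the corresponding non-AZM arm group, then we will conclude that the AZM group is superior to the non-AZM group".

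Sample size and power analysis writes the two hypotheses out separately: "This study is powered to test the hypothesis that HCQ + AZM improves recovery rate compared to HCQ alone", and likewise "CQ + AZM improves recovery rate compared to CQ alone". It gives one alpha, 0.05, for both and states that "we plan on enrolling a total of 500 participants (125 per arm) which would give us just over 80 percent power", quantified as 82%.

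The document contains no alpha split, testing order, stepwise procedure or global test, and gives no reason for leaving the two comparisons unadjusted.

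**The concern.** The plan allows two chances at one conclusion. Either pair can deliver it at the full 0.05, so a drug that does nothing has two independent opportunities to appear to work. In a trial described as phase III, the error rate of the success rule should be known and controlled. Here it is neither stated nor held at the level of a single test.

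The breadth of the conclusion is also left loose. The rule ends with "then we will conclude that the AZM group is superior to the non-AZM group" and does not name the backbone on which the difference was seen.

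**Working it through.** **Inputs from the document**
- Two comparisons across four separately randomized arms, 1:1:1:1, with no shared control (Randomization Procedures; Primary endpoint analysis).
- Two-sided 0.05 per comparison, with the claim made only when AZM is faster: 0.025 in the direction that matters.
- 125 per arm; medians 11 and 7 days; censoring 0.04 per day (Sample size and power analysis); follow-up censored at 42 days (Primary endpoint analysis).

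**Assumptions not in the document:** exponential recovery times and a log-rank test. They affect the power figures only.

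**1. Reproduce the stated 82%.** Hazards are ln2/11 = 0.0630 and ln2/7 = 0.0990 per day, so the hazard ratio is 11/7 = 1.571. Expected events per arm are 125 × λ/(λ + 0.04) × (1 − exp(−42(λ + 0.04))). This gives 75.5 and 88.8, or 164.2 per pair after rounding.
- Schoenfeld: z = √164.2 × ln(1.571)/2 = 2.896. Power is Φ(2.896 − 1.960) = 82.5% at 0.05 and Φ(2.896 − 2.241) = 74.4% at 0.025.
- Freedman: z = √164.2 × 0.571/2.571 = 2.848. Power is 81.3% at 0.05 and 72.8% at 0.025.

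The stated 82% is therefore per-comparison power with the full 0.05 given to each hypothesis.

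**2. Error of the rule as written, AZM without effect on either backbone.**
- At least one false superiority claim: 1 − (1 − 0.025)² = 4.94%, against 2.5% for one test.
- Counting significant results in both directions: 1 − 0.95² = 9.75%, against 5%.
- Patient-level log-rank simulation of the design (200,000 trials): 2.6% for one pair and 5.0% for either. A separate run of 40,000 gave 2.7% and 5.3%, with a correlation of 0.003 between the two statistics.

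**3. Error with Hochberg at familywise two-sided 0.05.** Under the null, each comparison favours AZM with P < 0.025 with probability 0.0125, favours AZM with P from 0.025 to 0.05 with probability 0.0125, and is significant against AZM with probability 0.025.
- At least one P < 0.025 in favour: 1 − 0.9875² = 2.484%.
- Both in the 0.025 to 0.05 band in favour: 0.0125² = 0.016%.
- One in that band, the other significant against AZM: 2 × 0.0125 × 0.025 = 0.063%.
- Total: 2.56%. The small excess over 2.5% comes from the last line. Holm gives 2.484% + 0.016% × 2 = 2.52%.
- If only one effect is real, the false claim on the other backbone is 2.5% unadjusted and 0.0125 + 0.0125 × 0.825 = 2.28% with Hochberg.

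**4. Power per comparison with Hochberg.** This is power at 0.025, plus (power at 0.05 − power at 0.025) × the probability that the other comparison has P < 0.05.

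| | Unadjusted | Both effects real | Only one real |
|---|---|---|---|
| Schoenfeld | 82.5% | 74.4 + 8.2 × 0.825 = 81.1% | 74.4 + 8.2 × 0.05 = 74.8% |
| Freedman | 81.3% | 72.8 + 8.5 × 0.813 = 79.7% | 72.8 + 8.5 × 0.05 = 73.2% |
| Simulation | 82.0% | 80.5% | 74.1% |

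Holm, by Schoenfeld, gives 80.4% and 74.6%.

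**The case against.** The strongest reply is that these are two separate questions in disjoint patients, much like two separate trials, and that many statisticians would not adjust. The rule compares each AZM arm with its corresponding arm, and the power section writes the two hypotheses separately. Read in that way, each claim keeps its own 2.5%. The word *either* does not itself create the 4.9%; two separate sentences at 0.05 would give the same figure. This stands, and it limits the point to the joint rule. It does not remove the point, because the plan does not take that position. It frames one null hypothesis, joins the two tests in one rule and draws one conclusion, without giving a reason for not adjusting.

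Three stronger readings are tempting, and the document does not support them:
- *That one win is meant to establish AZM in general.* The wording does not exclude this, but the reference to the corresponding arm makes the pair-specific reading the more natural one.
- *That the chance of a false superiority claim is 9.75%.* That figure includes results in which AZM is slower, which cannot trigger the claim.
- *That the test level is still open and could be chosen after the results.* The rule fixes 0.05 and the direction, and 82% reproduces only at an unsplit 0.05.

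It is also fair to say that the false-claim rate stays just under 5%, and that adjustment gains little (2.5% to 2.3%) once one of the effects is real.

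**Conclusion.** The concern holds for the joint rule. If AZM has no effect on either backbone, the chance of at least one false superiority claim is 4.9% against 2.5% for one test, nearly double (two-sided, 9.75% against 5%). This rests only on independence, which follows from four separately randomized arms with no shared control, and on each test holding its nominal level. A claim strictly limited to its own backbone carries 2.5%.

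The stated 82% is not wrong. It is per-comparison power at an unadjusted 0.05, which the plan does not say. The rule should be corrected before results are seen, but the point does not call the design or the sample size calculation into question. The HCQ vs CQ and HCQ + AZM vs CQ + AZM comparisons are also unadjusted, but they do not feed the AZM conclusion and lie outside this point.

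**What to change.** In Primary endpoint analysis, replace the sentence containing the either-arm rule with text such as:

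> The two AZM comparisons will be tested with the Hochberg procedure at a familywise two-sided alpha of 0.05. If both P-values are below 0.05, both are significant; otherwise a comparison is significant only if its P-value is below 0.025. Superiority of adding AZM will be concluded only for the backbone (HCQ or CQ) whose comparison is significant in favour of AZM.

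Holm is an acceptable alternative. Limiting the claim in words alone, without adjustment, would make the plan clearer but leave the 4.9% in place.

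In Sample size and power analysis, state that 82% is per-comparison power at an unadjusted 0.05. Add the Hochberg figures with their assumptions (exponential times, log-rank test): about 80-81% if both effects are as assumed and about 73-75% if only one is real.

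Cost: the change is to text only, and no added patients are proposed. Per-comparison power falls by about 1.5 points if both effects are real (82.5 − 81.1 = 1.4; Freedman 81.3 − 79.7 = 1.6), which by Freedman lands just under 80%. It falls by about 8 points if only one effect is real (82.5 − 74.8 = 7.7; Freedman 81.3 − 73.2 = 8.1).

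### The HCQ v CQ question is put to two half-trial comparisons with no pooled test or reading rule; one AZM-stratified comparison would answer it with more power

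*Combined protocol and SAP*

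**What the plan says.** Statistical Considerations sets out what is primary: "The primary hypotheses in this study are whether the addition of AZM to either HCQ or CQ improve patient recovery rates". The Primary endpoint analysis section agrees. Its null hypothesis is "no difference in recovery rates between the non-AZM treatment arms and the AZM treatment arms (HCQ vs HCQ + AZM, CQ vs CQ + AZM"), and its decision rule asks whether either AZM arm should "have significantly faster recovery rates (two-sided" P below 0.05) than its own non-AZM arm.

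After that rule the same section continues: "We will also compare recovery rates between the HCQ vs CQ, and HCQ + AZM vs CQ + AZM treatment arms to assess whether HCQ and CQ" have different effects on recovery. The plan says nothing more about the HCQ v CQ comparison. It gives no significance level, no secondary or exploratory label, no combined test, and no statement of how to read one significant and one non-significant result. The section on secondary and exploratory endpoint analyses does not mention it.

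The sample size section covers only the AZM contrasts: "This study is powered to test the hypothesis that HCQ + AZM improves recovery rate compared to HCQ alone, and CQ + AZM improves" on CQ alone.

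**The concern.** The sentence poses one question, whether the two backbone drugs differ, and sends it to two comparisons on disjoint arms: arm 1 v arm 3, and arm 2 v arm 4. Each uses half of the 500 patients.

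Two consequences follow. First, with no reading rule, either nominally significant result could be presented as evidence that one drug is better. Second, if a real backbone effect is much the same with and without AZM, splitting the data loses power and often leaves one comparison significant and the other not. The plan does not say what would then be concluded. The trial is open-label, so the rule is better fixed before results accumulate.

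**Working it through.** **Inputs.** From Sample size and power analysis: 125 per arm; "we assume 11 days as a rough estimate for median recovery time in the non-AZM treatment groups"; "Assuming a minimum improvement of 4 days in the median recovery time (median recovery time of 7-days"); censoring 0.04 per day; alpha 0.05. From Primary endpoint analysis: two-sided testing and censoring at 42 days. My assumptions: exponential recovery and censoring times; no AZM effect (slower backbone at a median of 11 days in both AZM strata); backbone hazard ratios (HR) of 1.2, 1.3 and 1.4, which the documents do not give.

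**Formulas.** Rate λ = ln 2 / median. Expected recoveries per arm = 125 × λ/(λ + 0.04) × [1 − exp(−42(λ + 0.04))]. Power for d events = Φ(½·√d·|ln HR| − 1.96).

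**The plan's own figure.** λ = ln 2/11 = 0.0630 gives 125 × 0.6036 = 75.5 events. λ = ln 2/7 = 0.0990 gives 125 × 0.7102 = 88.8. The total is 164.2 from unrounded values, with HR = 11/7 = 1.571. Power = Φ(½ × √164.2 × 0.452 − 1.96) = Φ(0.936) = 82.5%, which matches the stated 82%. The model is therefore a fair basis for the rest.

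**No backbone difference.** The two comparisons share no patients, so they are independent. If each is read at two-sided 0.05 and either counts, P(at least one false positive) = 1 − 0.95² = 9.75%. A simulation of 20,000 four-arm trials gave 9.85% with all arms equal and 10.2% with an AZM effect present. The single AZM-stratified log-rank test gave 5.0% and 4.8%.

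**A consistent backbone effect.** The stratified test combines both pairs, so it has 2d events. With p the power of each separate test, P(exactly one significant) = 2p(1 − p), P(both) = p² and P(neither) = (1 − p)².

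| Backbone HR | d per pair | Power, each test | Power, stratified (2d) | Exactly one | Both | Neither |
|---|---|---|---|---|---|---|
| 1.2 (assumed) | 156.6 | 21% | 36% | 33% | 4% | 63% |
| 1.3 (assumed) | 158.9 | 38% | 65% | 47% | 14% | 38% |
| 1.4 (assumed) | 161.1 | 57% | 86% | 49% | 32% | 19% |
| 1.571 (11 v 7 days) | 164.2 | 82.5% | 98.4% | 29% | 68% | 3% |

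Worked row, HR 1.3: ln 1.3 = 0.2624. Each test: Φ(½ × √158.9 × 0.2624 − 1.96) = Φ(−0.306) = 38%. Stratified: Φ(½ × √317.9 × 0.2624 − 1.96) = Φ(0.379) = 65%. Split: 2 × 0.380 × 0.620 = 47%.

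Simulation agrees. At 11 v 7 days exactly one test was significant in 29.5% of trials and stratified power was 98.2%. At 11 v 8.5 days (HR 1.29) the figures were 46% and 63%.

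**Against an either-test rule.** Counting either test as positive gives 1 − (1 − p)²: 37%, 62%, 81% and 97% for the four rows. The stratified test is about equal at HR 1.2 and higher in the other three rows, at about half the false-positive rate.

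**The case against.** The strongest reply is that these comparisons are not primary, so little hangs on them. A reader might infer from the section heading that they belong to the primary analysis. The documents do not support that. The stated primary hypotheses, the null hypothesis and the power calculation all concern adding AZM, and the decision rule comes before the backbone sentence and does not use it. The heading means analyses of the primary endpoint; the same section also contains a per-protocol analysis that it calls secondary. This stands in full, and for the same reason the backbone tests should not be added to the AZM pair to compute one error rate across four tests.

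It is also fair to say that the plan contains no rule under which either backbone test at 0.05 is a finding. The 9.75% is therefore conditional on a reading the plan leaves open.

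A reader might further infer that a split is the usual result, or that it could not be interpreted. Neither holds generally. A split is the single most likely outcome only from about HR 1.3 to 1.45. Below that range neither test is usually significant; above it both usually are (68% at 11 v 7 days). The plan also promises Cox hazard ratios with 95% confidence intervals for the treatment groups, and two similar estimates on either side of P = 0.05 can be read from their intervals.

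Finally, separate comparisons are a legitimate choice where an interaction is suspected. The plan does not give that reason, and its sentence asks one overall question. The loss of power from splitting the data remains.

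**Conclusion.** The point holds as an inexpensive improvement to a non-primary analysis. One question is answered by two half-trial comparisons with no pooled test and no rule for discordant results, although the same data allow a single stratified test using all 500 patients.

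If the backbone effect is consistent across AZM, each separate test gives up between 15 and 29 percentage points of power over the range examined, and exactly one is significant in 29% to 49% of trials. These figures rest on exponential times, the plan's 11-day median and censoring rate, and, except at 11 v 7 days, on assumed hazard ratios. The 9.75% false-positive rate rests on the further assumption of 0.05 per test with either counting.

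The AZM conclusion, the sample size and the power statement are untouched.

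**What to change.** Replace the backbone sentence with wording such as:

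*As a secondary analysis of the primary endpoint, the HCQ arms (1 and 2) and the CQ arms (3 and 4) will be compared once, by a log-rank test stratified by AZM at two-sided 0.05, with a stratified Cox hazard ratio and 95% CI. The comparisons within each AZM level will be reported descriptively, together with the backbone-by-AZM interaction.*

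The cost is this wording and one STRATA statement in the SAS procedures the plan already names; it needs no new patients or data. The downside is that if the backbone effect depends on AZM, the stratified test estimates an average, and opposite effects could cancel. That is why the two separate comparisons and the interaction stay in the report.

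Keeping two tests at 0.025 each would also control the error (1 − 0.975² = 4.94%), but power per test at 11 v 7 days would fall from 82.5% to 74.4%, so the stratified test is the better choice for a single overall question.

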## **STUDY AIMS/ENDPOINTS**

### **Primary**

1. Time (hours) from randomization to recovery defined as 1) absence of fever, as defined as at least 48 hours since last temperature  $\geq 38.0^{\circ}\text{C}$  without the use of fever-reducing medications AND 2) absence of symptoms of greater than mild severity for 24 hours AND 3) not requiring supplemental oxygen beyond pre-COVID baseline AND 4) freedom from mechanical ventilation or death

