#### *Sensitivity analyses*

In our primary analysis death is treated as a competing risk for recovery (i.e., someone that dies will never recover) by censoring subjects at their date of death. Although we anticipate low mortality rates (e.g., 1.4%) censoring patients due to death has the potential to bias recovery rate estimates. In order to assess this assumption we will explore the use of a more complex approach that explicitly models the subdistribution of recovery rate. If results from this analysis are substantially different from the primary analysis, then we will use model fit statistics and Monte Carlo simulation to determine whether the more complex model better describes the data generating process.

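### Censoring deaths makes Kaplan-Meier recovery proportions and medians slightly too favourable, and partial-likelihood fit statistics cannot settle a disagreement with the subdistribution analysis

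*Combined protocol and SAP*

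**What the plan says.** The primary endpoint (Study Aims/Endpoints) is time to recovery, and one of its four conditions is "freedom from mechanical ventilation or death".

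Under Primary endpoint analysis: "Our primary analysis will be to use Kaplan-Meier (KM) survival analysis", comparing each azithromycin (AZM) arm with its non-AZM counterpart at two-sided 0.05. If an AZM arm recovers significantly faster, "then we will conclude that the AZM group is superior to the non-AZM group". A Cox model follows, from which adjusted hazard ratios and confidence intervals are reported. On incomplete follow-up: "Participants that are lost to follow-up or die will be censored at the date of last contact or date of death, respectively". Patients still unrecovered at day 42 are censored then. PROC LIFETEST and PROC PHREG are the only procedures named.

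The Sensitivity analyses section opens by describing the handling of deaths: "In our primary analysis death is treated as a competing risk for recovery (i.e., someone that dies will never recover) by censoring subjects". The section gives 1.4% as an example of the low mortality expected. It accepts that "censoring patients due to death has the potential to bias recovery rate estimates", and says "we will explore the use of a more complex approach that explicitly models the subdistribution of recovery rate". It then sets a condition, "If results from this analysis are substantially different from the primary analysis", under which fit statistics and Monte Carlo simulation are to show whether the more complex model is closer to how the data arose. The section does not name a fit statistic, a threshold or a simulation design. It does not say what counts as a substantial difference, or what a difference would change in the superiority conclusion.

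**The concern.** There are two separate issues.

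**The curves.** By the plan's own account a patient who dies can never recover. Censoring that patient makes Kaplan-Meier treat him or her as someone who would have gone on to recover at the same rate as the survivors. A reader who takes 1 minus Kaplan-Meier as the share of patients who recovered gets too high a figure, and too short a median. The plan does not commit to a cumulative-incidence report, and it does not say whether a recovery rate means a hazard or a proportion.

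**The rule for a disagreement.** The death-censored analysis compares recovery hazards among patients still alive and unrecovered. The subdistribution analysis compares the cumulative share recovered, with the dead counted as not recovered. The two can differ when both are correctly specified, so a difference is not evidence that one fits badly. Letting fit decide between them replaces a choice of estimand with a comparison that, for the usual statistics, has a fixed outcome. At stake is whether the planned sensitivity analysis can inform anyone, and whether it is clear in advance which result governs.

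**Working it through.** **1. The plan's own power.** Inputs from Sample size and power analysis: medians 11 and 7 days, censoring 0.04 per day, 125 per arm. Follow-up is 42 days. Assume constant hazards.

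- Recovery hazards: ln2/11 = 0.0630 and ln2/7 = 0.0990 per day.
- Probability of an observed recovery: λ/(λ+0.04) × [1 − exp(−42(λ+0.04))] = 0.604 and 0.710.
- Events: 125 × 0.604 + 125 × 0.710 = 75.5 + 88.8, or 164.2 from unrounded values.
- Schoenfeld: √(164.2/4) × ln(11/7) − 1.96 = 2.896 − 1.960 = 0.936, so power is 82.5%. The plan states 82%.

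The 0.04 per day already includes death, so this is the power of the death-censored test.

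**2. Size of the Kaplan-Meier excess.** Let μ be a constant death hazard, set so that the stated share dies unrecovered by day 42, with no other loss.

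- Kaplan-Meier with deaths censored estimates 1 − exp(−42λ).
- The true share recovered is λ/(λ+μ) × [1 − exp(−42(λ+μ))].

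| Recovery median | Mortality | μ per day | 1−KM, day 42 | True share recovered | Excess (points) | True median (days) |
|---|---|---|---|---|---|---|
| 11 d | 1.4% | 0.00096 | 92.9% | 91.8% | 1.1 | 11.07 |
| 11 d | 7% | 0.00505 | 92.9% | 87.3% | 5.6 | 11.41 |
| 7 d | 1.4% | 0.00143 | 98.4% | 97.1% | 1.3 | 7.05 |
| 7 d | 7% | 0.00755 | 98.4% | 91.9% | 6.6 | 7.25 |

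The 1.4% is the plan's example. The 7% is an assumption: it is the top of the 2-7% overall case-fatality range in the background section, not a forecast for this trial.

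**3. Does the test suffer?** In 40,000 simulated null trials with 125 per arm, 25% of patients were severe (median recovery 30 days, others 9), deaths occurred only in the severe, and loss was 0.04 per day. The death-censored test rejected in 2.62% + 2.56% = 5.2% with 1.4% mortality in both arms, and in 2.85% + 2.35% = 5.2% with 1.4% against 2.8% under AZM. The effect on the test is negligible.

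**4. Why the fit comparison has a fixed outcome.** For either model the log partial likelihood is the sum over recoveries of βx_i − log Σ_j w_j exp(βx_j), taken over patients at risk.

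- Both models have the same recoveries, so the first terms are identical.
- With the same covariates they have the same number of parameters, so the AIC and SBC penalties are equal.
- In the death-censored model the sum runs over patients alive, unrecovered and under observation (w = 1). Fine-Gray keeps all of these and adds patients who died earlier, with positive weights.

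Every Fine-Gray denominator is therefore at least as large, and its log partial likelihood cannot exceed the other at any β, nor at the maximum. So −2 log L, AIC and SBC can never prefer Fine-Gray.

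Simulation illustrates this identity and is not separate evidence for it. With hazard ratio 11/7, mortality settings of 1.4% or 7% and loss of 0 or 0.04 per day, AIC favoured Fine-Gray in 0 of 14,368 trials where it was the true model and in 0 of 15,211 where the cause-specific model was true (trials with at least one death).

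**5. Other readings of the rule.** These were tried with mortality matched by arm between the two true models, loss 0.02 per day and 400 datasets per setting.

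- *Likelihood-ratio chi-square against each model's own null.* This can favour Fine-Gray, but it did so in about 80% of datasets when the cause-specific model was true.
- *Calibrating the AIC gap by simulation.* The gap separated the two truths with an area under the ROC curve of only 0.52 (7% setting) and 0.55 (15% setting, used only to extend the range).

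**The case against.** The case for leaving the text alone is substantial.

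- The bias is disclosed, and a subdistribution analysis is foreseen. This stands. What remains is that exploring it is not a commitment to run and report it.
- The plan commits to a test and to hazard ratios, not to recovery proportions at day 42 or Kaplan-Meier medians. This also stands: the excess matters only if such figures are read from the curves.
- At 1.4% mortality the two analyses will seldom part. In a simulation with a common death hazard, significance at 0.05 differed in 1-4% of trials at 1.4% mortality and in 3-10% at 7%.
- If the fit rule always returns the death-censored model, the prespecified primary analysis simply survives. True, but then the rule is no check, and it is better to say outright which analysis governs.

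A reader might infer three stronger things that the documents do not support. One is that the primary test is invalid; it is a sound comparison of cause-specific recovery hazards. Another is that excess deaths under AZM would be hidden; all-cause mortality is a listed secondary endpoint. The third is that the plan's rule favours the death-censored model under any fit statistic. The plan names none and adds simulation, so the fixed outcome is proved only for the partial-likelihood statistics.

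**Conclusion.** A minor point that holds within limits. Recovery proportions from the death-censored Kaplan-Meier curves are too high at day 42 by about 1 point at the plan's 1.4% mortality, and by about 6 to 7 points at an assumed 7%. Medians are too short by less than 0.1 day and by about 0.25 to 0.4 day respectively. These sizes assume constant hazards and no other loss. The primary comparison remains valid and the 82% power stands.

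The procedure for resolving a disagreement is not a valid selector. It asks fit to choose between two estimands, and for −2 log L, AIC and SBC with the same covariates the answer is fixed in advance. That the plan means these statistics is an inference from its naming PROC PHREG. The unspecified simulation step supplies no criterion that would rescue it.

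**What to change.** **Sensitivity analyses section.** Delete the sentence on fit statistics and simulation. Replace the exploratory wording with a Fine-Gray model and Gray's test for each AZM contrast, always run and always reported as a sensitivity analysis. State that the death-censored log-rank, which compares cause-specific recovery hazards, governs the superiority conclusion.

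**Primary endpoint analysis section.** Report recovery by arm as cumulative incidence to day 42, with death before recovery as a competing event, instead of 1 minus Kaplan-Meier. Show mortality by arm beside it.

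Do not make the superiority claim conditional on Gray's test. An unqualified claim would then need both tests, and simulated joint power is about 77% at 1.4% mortality and 75% at 7%, against about 80-81% for the death-censored test alone. The stated power would no longer apply.

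**Cost.** A few sentences, one extra analysis run and slightly lower reported recovery proportions. No new data and no change in sample size are needed.
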